**Version 3, March 30, 2018**

Organized by:	Russian Society for Prevention of Non-Infectious Diseases League of Clinical Research
Study sponsor	Pfizer Ltd.
Project title	The program to assess the influence of routing and in-depth consultation of patients with cardiovascular risk factors on the choice of medicine and treatment compliance.
Short title of the project	3P (Primary Prevention Program)
Study type	A pharmacoepidemiological study (evaluation of specifics of the use and the effects of drugs in a large patient number in the real world medical settings).
Methodology of the study	
A systematic collection of retrospective and prospective data based on non-interventional patient observation, aimed to assess the risks, course and outcomes of a disease or a group of diseases:
 

• the retrospective part: database of patients with cardiovascular risks;

• the prospective part: observation of patients in the real world medical practice.

 
The research program will have two parts:
 

• The main part of the program (from the beginning of treatment to month 6): subjects with cardiovascular risk will be followed for 6 month after administration of treatments to reduce the risks. All study sites that have consented to participated in this research project, will take part in this study phase

• A 6-month extension of the main program (from month 6 to month 12): subjects with the risk of cardiovascular disease will be followed for additional 6 months after the end of the main part of the program (from month 6 to month 12 after administration of treatments to reduce the risks). All study sites that have consented to participated in the 6-month extension of the research project can take part in this extension.

Background and rationale	
It is common that subjects with the risk of cardiovascular disease do not have proper preventive care.
 
Cardiovascular disorders are known to be the leading cause of death

in Europe. About 4,3 million people die annually from these diseases. In November 2010, the results of a large European study were released that showed that an improvement of preventive care can substantially reduce cardiovascular mortality.

The Epidemiological study of European Cardiovascular Risk patients: Disease prevention and management in usual daily practice aimed at evaluation of the influence of cardiovascular risk factors on mortality. In addition, the investigators assessed how successful was the management of these risk factors. The results obtained confirmed an increase of cardiovascular mortality in the presence of one or more risk factors (smoking, arterial hypertension, diabetes mellitus, increased cholesterol levels and obesity). It raises concern that in everyday clinical practice these factors are not adequately managed, that may be a cause of the rise in cardiovascular mortality.

Hyperlipidemia is the second (after arterial hypertension) cause of early mortality in Russia. Hyperlipidemia can be associated with both increased low density lipoprotein cholesterol and triglyceride levels. Hypercholesterolemia is a confirmed risk factor of atherosclerotic cardiovascular disease and its complications.

### **Objectives of the project**

1. To make physicians (internists, cardiologists, medical specialists working in preventive facilities) familiar with current approaches to assessment of cardiovascular risks and their management through timely administration of corresponding treatments, by organization of training activities (web conferences, meetings, round table discussions).
2. To inform physicians, especially those in primary care, on the importance of a thorough assessment of cardiovascular risks and timely administration of therapy.
3. To analyze databases currently effective in medical institutions (those on healthy subjects and patients) in order to identify subjects with cardiovascular risk factors.
4. To assess blood lipids in subjects with suspected high cardiovascular risk.
5. To perform in-depth medical consultations of subjects on the importance of primary cardiovascular prophylaxis, including by means of preventive statin treatment (with the information on original drugs and generics, social programs by manufacturers implemented in pharmacies).
6. To assess efficacy of the combination of preventive activities (in-depth medical consultation of patients on their treatment; sms reminders on the necessity to comply with their doctor's prescriptions) on patients' compliance to treatment.
7. To follow changes in cardiovascular risk factors with associated assessment of patients' compliance to medical recommendations.

### **Number of study sites**

6 (Kazan, Novosibirsk, Omsk, Samara, St. Petersburg, Ufa).

Patient number	The target patient number is 12,000.
Study period	
Development and approval of the project materials (protocol, electronic database): March 31, 2017.
 
Start-up meeting: April 2017.
 
Preparation, printing and delivery of the project materials: April 30, 2017.
 
First patient in: May 1, 2017.
 
Last patient in: April 30, 2018.
 
End of data collection for the main part of the program: October 30, 2018.
 
Analysis of the results and preparation of the final study report on the main part of the program: December 31, 2018.
 
End of data collection for the 6-month extension phase: April 30, 2019.
 
Analysis of the results and preparation of the final study report: June 30, 2019.

Study condition	
Cardiovascular risk factors.
 
Special attention will be given to lipid level assessments.

Study treatment	Statins included into the list of life-saving and essential drugs and administered for correction of lipid spectrum to prevent cardiovascular disorders in the real world medical setting.
Ethical and regulatory aspects	
The state registration of the project is planned to be done in the Federal State Research Institution “Center of Informational Technologies and Executive body systems” of the Ministry of Education and Science of the Russian Federation, in accordance with the Act of the Government of the Russian Federation №279 from March 31, 2009.
 
It is planned to establish a Research and Advisory Committee for the project.
 
It is planned that the study materials will be approved by an Intercollegiate Ethics Committee.
 
Personal data management in the project will be done in accordance with the Federal Law 152-F3 from July 27, 2006 (version of June 4, 2014).
 
The Russian Society for Prevention of Non-Communicable Diseases and the League of Clinical Research will receive blinded data on the study subjects, i.e. the participating study sites will implement the blinding procedure on personal data (Art. 3, par.9, 152-F3).
 
To improve data quality, monitoring activities will be implemented in the main part of the program, in accordance with normative requirements on performance of research as follows:
 
 
• The National Standard of the Russian Federation from
 

27.09.2005 GOST R 52379-2005 “Good Clinical Practice”,

- The Decree of the Ministry of Health and Social Development of Russia №757n from 26.08.2010 r. “On approval of the Order of pharmacovigilance monitoring of safety of pharmaceuticals for medical use, registration of adverse effects, serious adverse reactions, unexpected adverse reactions during the use of pharmaceuticals for medical use”.

The monitoring will be performed by an independent third party (a contract research organization) and will include (but not limited to) visits of study monitors to study sites and check-ups of the study materials.

**Criteria and methodology of medical chart selection for further screening**

- Total cholesterol  $\geq 5$  mmol/L
- Additional risk factors identified during previous screening:
  - age 40-65 years
  - arterial hypertension (SBP $>140$  mmHg, DBP $>90$  mmHg) or antihypertensive treatment
  - history of dyslipidemia
  - smoking
  - overweight or obesity (BMI  $\geq 25,0$ )
  - diabetes mellitus
  - chronic renal disease.

**Inclusion criteria**

Data on the following subjects is planned to be collected in the project:

- Aged from 40 to 65 years inclusively
- With a high ( $\geq 5\%$ ) cardiovascular risk measured by SCORE and low density lipoprotein (LDL) levels of  $\geq 2,5$  mmol/L, or with a very high ( $\geq 10\%$ ) cardiovascular risk measured by SCORE and LDL levels  $\geq 1,8$  mmol/L or With atherosclerotic stenosis of brachiocephalic arteries of  $>50\%$  in the absence of cerebrovascular disease

**Exclusion criteria**

- No contraindications to statin treatment and not taking statins at study entry.
- History of the following clinically significant events and conditions:
  - (a) myocardial infarction
  - (b) stroke
  - (b) transient ischemic attack
- Presence of the following diseases at the time of a statin administration:

 SCORE: Systematic COronary Risk Evaluation.

 If atherosclerosis of brachiocephalic arteries has been confirmed either by data obtained from the source medical documentation or identified during the work-up within routine medical care of the medical institution; decision to perform such a work-up can be made by a doctor and is unrelated to performance of the given research project.

- (a) ischemic heart disease
- (b) heart failure
- (b) peripheral artery atherosclerosis
- (c) atherosclerotic stenosis of brachiocephalic arteries with cerebrovascular disease.

Subjects must give their consent for processing of their personal data for the purposes of this scientific project.

**Data to be collected**

- Demographic characteristics
  - (a) gender
  - (b) age (full years by the time when written informed consent is signed)
- cardiovascular risk factors:
  - (a) hypercholesterolemia (based on the results of lipid tests, see below)
  - (b) smoking status (yes/no)
  - (c) blood pressure (systolic blood pressure, mmHg; diastolic blood pressure, mmHg)
  - (d) diabetes mellitus (yes/no)
  - (e) height (at Visit 1) and weight (at all visits) for calculation of body mass index (BMI)
- blood lipids (all in mmol/L):
  - (a) total cholesterol
  - (b) low density lipoprotein cholesterol
  - (c) high density lipoprotein cholesterol
  - (d) triglycerides
- treatment administered for prevention of cardiovascular disease:
  - (a) statin prescribed for prevention of cardiovascular disease (name; original /generic; dose mg/daily)
  - (b) other treatments prescribed for prevention of cardiovascular disease (name; original /generic)
  - (c) if a drug is withdrawn, the reason for withdrawal:
    - by prescribing physician due to low efficacy;
    - by prescribing physician due to poor tolerance;
    - by another physician due to any reason;
    - unavailability of the drug;
    - patient's decision;
    - other reasons
  - (d) duration of statin therapy, months,
  - (e) proportion of subjects who continue to take statin by the end of the main part of the program (6 mo) and by the end of the 6-mo extension of the main program (12 mo)
  - (f) Morisky-Green test, scores (see Appendix 1).
- development of one of the following conditions (disorders) during the trial:
  - (a) myocardial infarction (yes; no)
  - (b) stroke (yes; no)
  - (c) transient ischemic attack (yes; no)

---

 If cerebrovascular disease is present, statin administration cannot be considered as primary prevention.

- (d) ischemic heart disease (yes; no)
- (e) heart failure (yes; no)
- (f) atherosclerosis of brachiocephalic arteries (yes; no)
- (g) hospitalization (yes; no; if yes, due to a cardiovascular disease or due to another reason)
- (h) emergency call (yes; no; if yes, due to a cardiovascular disease or due to another reason)
- (i) revascularization (yes; no)
- (j) death (if yes, due to a cardiovascular disease or due to another reason).

**Time points of assessments**

In this study data obtained in the real world medical practice will be analyzed. It is assumed that subjects will be assessed and treated according to the usual practice of their medical centers and at a physician's discretion.

It is desirable that the standard medical practice of the participating study sites involves regular assessment of patients who have been administered statins for improvement of their lipid spectrum to prevent cardiovascular diseases. It is assumed that patients to whom a statin has been prescribed for prevention of cardiovascular diseases should be assessed approximately at 1 to 2, 3 to 4, 5 to 6, and 11 to 12 months to monitor their treatment compliance, potential treatment modifications, course of their cardiovascular risks or cardiovascular disorders.

Since this research project is aimed to assess the examination and treatment of patients in the real world medical practice, the study organizers will not set any concrete time points at which patients should make their visit to the doctor. The type of the follow-up should correspond to that adopted in the medical institution.

At the same time, it is desirable that during the main part of the program those subjects that have been prescribed a statin, would see their doctors three time, approximately at 1 to 2, 3 to 4, and 5 to 6 mother after initiation of statin treatment. Those participating in a 6-month extension of the main part of the program are recommended to be assessed at 11 to 12 months after initiation of statin treatment.

**Data management and analysis**

Remote input of data (data into the electronic database will be entered by the participating physicians from the workplace). Data will be entered in depersonalized form.

The methods of descriptive statistics will be used for the whole population for all the indicators studied.

For those categories for which it is possible (for example, "high-density lipoprotein cholesterol"), the data will be reduced to time points "after 2 months"; "in 3 months"; "in 6 months"; "in 12 months", using the method move forward the last observation data (Last Observation Carried Forward, LOCF).

In addition, using descriptive statistics methods, all the studied indicators will be analyzed separately for the following populations:

- population in which a set of preventive measures was carried out (in-

depth medical advice to patients about taking therapy, sms reminders about the need to follow the doctor's prescription)

- population in which a set of preventive measures was not carried out.

Using the methods of comparative statistics, the following variables will be compared:

- Change in the lipid spectrum of the blood during the study period:  
(A) in the whole population  
(B) in a population in which a set of preventive measures was carried out (in-depth medical advice to patients about taking therapy, sms-reminders about the need to follow the doctor's prescription)  
(C) in a population in which a set of preventive measures was not carried out.

In addition, using the methods of comparative statistics, the following indicators will be compared:

- reasons for withdrawal of therapy
- duration of statin therapy: between groups; for each trade name
- Percentage of patients who continued to receive statins at the end of the main part of the program (6 months): between groups; for each trade name
- Percentage of people who continued to receive statins at the end of the 6-month continuation of the main part of the program (12 months): between groups; for each trade name
- results of Moriski-Green test
- blood pressure
- smoking status
- change in body mass index
- development of one of the following conditions (occurrence of the following diseases, development of the following events) during the study period:  
(A) myocardial infarction  
(B) stroke  
(C) transient ischemic attack  
(D) ischemic heart disease  
(E) heart failure  
(F) atherosclerosis of brachiocephalic arteries  
(G) atherosclerotic disease of peripheral arteries  
(H) hospitalization  
(I) call an ambulance  
(K) revascularization  
(K) death,

in a population in which a set of preventive measures was carried out (in-depth medical advice to patients about the admission of therapy, sms-reminders about the need to follow the doctor's prescription), and in a population in which a set of preventive measures was not carried out.

At the end of the study, a final report will be prepared in Russian.

**General description of the study** 6 centers of medical prevention (MSC), located in different regions of Russian Federation will take part in this project, in cooperation with other medical and preventive institutions.

During the **first** phase of the project (screening 1) is expected to be screened in the existing health care institutions of primary health care databases (patients, healthy individuals) and identify individuals;

- (a) not currently suffering from cardiovascular disease (diseases), which are exclusion criteria for this scientific program,
- (b) do not have the history of conditions (diseases), which are exclusion criteria in this scientific program,
- (c) not receiving statin for the prevention of cardiovascular disease,
- (d) having risk factors for cardiovascular disease.

Sufficient number of subjects should be screened in each center to include 2,000 patients who meet the inclusion and exclusion criteria in the project.

During the **second** phase of the project (screening 2) subjects will be invited to the study centre in medical prevention and treatment-and-prophylactic institutions (MPI), or to physician to confirm that subject:

- (a) does not currently suffer from cardiovascular disease (diseases), which are exclusion criteria for this scientific program,
- (b) does not have a history of conditions (diseases), which are exclusion criteria for this scientific program,
- (c) does not receive statins for the prevention of cardiovascular diseases,
- (d) has risk factors for cardiovascular disease,
- (e) has reasonable indications for determining the lipid spectrum.

During the **third** phase of the project (screening 3) subjects who were selected during the second phase, will be determined lipid profile by express test.

Persons with lipid metabolism disorders, which are indications for prescribing vital and essential statins for the prevention of cardiovascular diseases, are prescribed statins in accordance with standard practice of medical institution.

Following the appointment of statin subject signs an informed consent for processing of personal data. From this moment, the subject is considered included in the scientific research.

It is necessary to include 2,000 patients in each center that meet the inclusion and exclusion criteria.

During the **fourth** phase (the main part of the program - observation):

- (a) all subjects will be consulted about the prevention of cardiovascular diseases and the use of medicines for this purpose
- (b) subjects will be randomized (using the CRStat system) in two groups in a ratio 1: 1; in one of the groups will be carried out a profound consultation (different from standard practice for this medical institution) on the importance of primary prevention of cardiovascular diseases, including preventive reception of statins
- (c) subjects in profound consultation group will receive regular reminders (2 times a month) via SMS and calls to check maintenance the doctor's recommendations and follow-up visit to study centre
- (d) subjects will come for final examinations (consultations) to study doctor.

During the **fifth** phase (6-month continuation of the program - observation):

- (a) subjects in profound consultation group will receive regular reminders (2

times a month) via SMS and calls to check maintenance the doctor's recommendations and follow-up visit to study centre  
(b) subjects will come for the final examination (consultation) to study doctor.

It is desirable that medical prevention and treatment-and-prophylactic institutions (MPI) take part in the program, in which standard medical practice involves periodic surveys of persons receiving statins for lipid correction and for prevention of cardiovascular disease: approximately in 1-2, 3-4, 5-6 and 11 -12 months after beginning of statin therapy.

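### The month-3 LOCF point sits at the start of the 3-to-4-month visit window, so as written it would use only a minority of second-visit values

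*Protocol*

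**What the plan says.** The Time points of assessments section says that patients prescribed a statin "should be assessed approximately at 1 to 2, 3 to 4, 5 to 6, and 11 to 12 months". The General description of the study repeats the schedule: "approximately in 1-2, 3-4, 5-6 and 11 -12 months after beginning of statin therapy". These are expectations, not fixed dates, since "the study organizers will not set any concrete time points at which patients should make their visit to the doctor".

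The Data management and analysis section then places repeated measures on a common time scale. Where a measure allows it (HDL cholesterol is the example given), "the data will be reduced to time points 'after 2 months'; 'in 3 months'; 'in 6 months'; 'in 12 months", and this is done "using the method move forward the last observation data (Last Observation Carried Forward, LOCF".

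The first item listed for comparative analysis is "Change in the lipid spectrum of the blood during the study period", in the whole population and in the groups with and without the preventive measures. The protocol gives no rule that ties a particular visit to a particular time point.

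**The concern.** There are four expected visits and four analysis points, and three of the points follow one pattern: each stands at the close of its visit window, so a visit made inside the window is already there to be used. The second point breaks the pattern. It stands where its window opens, so a patient seen at, say, 3.5 months has no second-visit value yet. LOCF then supplies the value from the first follow-up visit, or baseline if that visit was missed.

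At stake is the month-3 summary of lipids and similar measures. It would be drawn towards the earlier level, and part of any change between the first and second follow-up visits would be hidden by the data rule. Most second-visit measurements would contribute nothing for patients who also attend at 5-6 months.

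**Working it through.** **Inputs from the protocol**

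| Visit | Expected window (months) | LOCF point (month) | Position of the point |
|---|---|---|---|
| 1 | 1-2 | 2 | upper end |
| 2 | 3-4 | 3 | **lower end** |
| 3 | 5-6 | 6 | upper end |
| 4 | 11-12 | 12 | upper end |

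The windows come from Time points of assessments and the LOCF points from Data management and analysis. Taking the upper end of each window would give 2, 4, 6 and 12. The stated 2, 3, 6 and 12 does not follow from the schedule in that way.

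**Quantity checked.** The share *p* of patients whose own second visit is at or before the analysis point, among those who attend that visit. The protocol gives no visit-time distribution, so the spreads below are assumptions.

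*Uniform visit times with slack s on each side of the window*, that is, over (3 − s, 4 + s), a length of 1 + 2s:

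- at month 3: p = s / (1 + 2s)
- at month 4: p = (1 + s) / (1 + 2s)

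*Normal visit times around the midpoint 3.5 with standard deviation σ*:

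- at month 3: p = Φ((3 − 3.5)/σ)
- at month 4: p = Φ((4 − 3.5)/σ)

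| Assumed spread | p at month 3 (as written) | p at month 4 |
|---|---|---|
| Uniform, s = 0 | 0/1 = 0% | 1/1 = 100% |
| Uniform, s = 0.25 | 0.25/1.5 = 17% | 1.25/1.5 = 83% |
| Uniform, s = 0.5 | 0.5/2 = 25% | 1.5/2 = 75% |
| Uniform, s = 1 | 1/3 = 33% | 2/3 = 67% |
| Normal, σ = 0.25 | Φ(−2) = 2% | Φ(2) = 98% |
| Normal, σ = 0.5 | Φ(−1) = 16% | Φ(1) = 84% |
| Normal, σ = 1 | Φ(−0.5) = 31% | Φ(0.5) = 69% |

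A simulation of 400,000 visit times per case agrees with these values. The month-4 column also gives the shares at months 2, 6 and 12 under the same spread, because those points already close their windows.

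*A case more favourable to month 3.* If sites recall patients at 3.0 months with symmetric scatter, p = Φ(0) = 50%.

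**Effect on the summary.** Suppose every patient has a first-visit value by month 2, and visit timing is unrelated to the lipid level. The month-3 mean is then p × (second-visit mean) + (1 − p) × (first-visit mean). The step shown from month 2 to month 3 is p times the step between the two visits: none of it at p = 0, a quarter at p = 0.25, a third at p = 0.33 and half at p = 0.5.

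**The case against.** The strongest reply is that the four time points are nominal names for the four visits, listed in the same order, with LOCF filling in a missed visit. On that reading the 3-4 month visit is the month-3 value and nothing is displaced. This is possible, and a statistical analysis plan that is not shown may say so. But the protocol does not say it. It names specific months and a carry-forward method, and a plan that mapped visits to windows would be correcting this text, not merely adding detail to it.

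The second reply is that visits are approximate and not mandated, so 3.0 and 4.0 are not hard limits. This stands, and it is why the result is a range and not a single figure.

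A reader might infer more than the documents support:

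- *That month 3 merely copies month 2.* This needs visits to fall almost wholly after month 3.0. With slack or early recall, a quarter to a half of patients have a new value. A first visit that runs past month 2 would also enter at month 3.
- *That second-visit data never appear.* A second-visit value is carried to month 6 if the 5-6 month visit is missed, and to month 12 if no later visit takes place. Visits made by month 3.0 are used at month 3.
- *That the trial's main comparisons are compromised.* Statin continuation is compared at 6 and 12 months, and lipid change is compared over the study period with no month-3 contrast named.

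**Conclusion.** The analysis points and the visit schedule do not match at the second visit, and this can be seen on the face of the protocol. Under a literal reading, the month-3 summary would use the second visit for about 0% to 33% of attending patients when visits spread over or around the stated window, and for about 50% if sites recall at 3.0 months. A point at month 4 would use it for 67% to 100% under the same window spreads. These percentages rest on assumed visit-time distributions; the position of month 3 at the lower edge of its window does not.

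The consequence is limited to one intermediate time point for lipids and similar repeated measures, whose summary would lean towards the earlier value. The mismatch does not alter the 2-, 6- and 12-month results. It is worth correcting because it is a stated rule that works against the protocol's own schedule.

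**What to change.** Either of two changes to the Data management and analysis section would do.

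1. Replace the analysis point 'in 3 months' with 'in 4 months', so that all four points close their visit windows. This changes one number. It makes the points consistent, but at each of them a visit that runs late would still be missed (17% to 33% of visits under the uniform slack cases above).
2. State that each visit is assigned to its window (1-2, 3-4, 5-6, 11-12 months), that visits falling between windows are allocated by a stated cut-point, and that LOCF is used only when a window has no visit. This takes a sentence or two and also deals with slightly late visits at the other points.

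The second is the more complete. Neither alters the visit schedule, the data collected or the number of patients.

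### LOCF is fixed up to month 12 although months 6 to 12 are optional by site and no visit times are set, so month-12 lipid summaries may contain values from month 6 or earlier and on-statin values of patients who have stopped

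*Protocol*

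**What the plan says.** The rule stands in the protocol, Data management and analysis. It covers measures described as "For those categories for which it is possible", with HDL cholesterol as the example. The values at all four time points are obtained by one method, namely "using the method move forward the last observation data (Last Observation Carried Forward, LOCF". The last of those time points is month 12, and the sentence attaches no condition to it. The same section describes all indicators for the whole population and by arm. It also lists "Change in the lipid spectrum of the blood during the study period" for the whole population and for those with and without the preventive measures. It sets no limit on who receives a month-12 value or on how old a carried value may be, and it makes no distinction by statin status.

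Other sections describe the follow-up that feeds this rule:

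- Methodology of the study, on months 6 to 12: "All study sites that have consented to participated in the 6-month extension of the research project can take part in this extension".
- Time points of assessments: "the study organizers will not set any concrete time points at which patients should make their visit to the doctor". Assessment is assumed "approximately at 1 to 2, 3 to 4, 5 to 6, and 11 to 12 months", and the last of these visits is tied to the extension: "Those participating in a 6-month extension of the main part of the program are recommended to be assessed at 11 to 12 months".
- General description of the study: about 2,000 patients per centre, randomised 1:1. Only the in-depth consultation arm receives SMS and call reminders, which also cover follow-up visits. In both the fourth and fifth phases, subjects are to come for final examinations.
- Data to be collected: drug withdrawal with its reason, and duration of statin therapy in months.

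**The concern.** LOCF is harmless only if an old value is a fair stand-in for the current one. Two features of this design work against that.

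First, a site outside the extension has no planned observation after month 6. Under the rule as written its patients would still have a month-12 lipid value, copied from month 6 or earlier.

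Second, the project studies compliance, so stopping the statin is central to its question. LOCF is triggered by a missing test, not by stopping. A stopper who is retested is handled correctly, whereas one who is not retested keeps the last value. If that value was taken on statin, a fall that may have been lost is reported as lasting. Because only one arm is reminded of visits, the untested share may differ by arm.

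At stake are the month-12 lipid summaries, overall and by arm, and any comparison of lipid change between arms that draws on them.

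**Working it through.** **The protocol's own figure.** 6 centres × 2,000 patients = 12,000, which agrees with the stated target. The protocol gives no rates of site opt-out, missed tests or statin stopping. Everything below other than the 6, 2,000 and 12,000 is therefore an assumption.

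**Part 1: sites outside the extension.** Each non-joining centre is 2,000/12,000 = 17% of the planned sample. Let f be the share of month-12 values copied from month 6, and a the true 12-month fall divided by the 6-month fall. The relative overstatement of the month-12 fall is f × (1/a − 1).

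| Centres not joining | f | a = 0.9 | a = 0.8 |
|---|---|---|---|
| 0 | 0 | 0% | 0% |
| 1 | 1/6 | 1.9% | 4.2% |
| 2 | 1/3 | 3.7% | 8.3% |
| 3 | 1/2 | 5.6% | 12.5% |

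Centres work with other institutions, so the unit that opts out may be smaller than a centre. For 600 patients (5%) the figures are 0.6% and 1.2%.

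**Part 2: untested stoppers.** Work in units of the on-statin fall. Let s be the share stopping, r the share of the fall lost off statin, m the share of stoppers untested, and q the share of untested stoppers whose last test was on statin. For the rest, the baseline value is carried.

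- True fall = 1 − s·r
- LOCF = (1 − s) + s[(1 − m)(1 − r) + m·q]
- Missing-at-random model without statin status = [(1 − s) + s(1 − m)(1 − r)]/(1 − s·m)
- Return to baseline = (1 − s) + s(1 − m)(1 − r)
- Untested stoppers imputed from tested stoppers = (1 − s) + s(1 − r) = the true fall, if the two groups are alike

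With s = 0.2, r = 1, m = 0.5, the true fall is 0.80:

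- LOCF: 0.90 (+12.5%) at q = 1; 0.85 (+6.25%) at q = 0.5; 0.80 (0%) at q = 0.
- Model without statin status: 0.80/0.90 = 0.889 (+11.1%) at every q.
- Return to baseline: 0.80 (0%).

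With s = 0.1 or 0.4 and q = 1, LOCF gives +5.6% or +33.3%. If lipids return only half way (r = 0.5, s = 0.2, m = 0.5, q = 1), the true fall is 0.90. LOCF then gives +5.6%, the model +4.9% and return to baseline −5.6%.

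**Contrast between arms.** Assume 30% stop in the control arm and 20% in the reminded arm, with r = 1 and q = 1. The true difference is 0.30 − 0.20 = 0.10. The table shows the share of it that each method recovers. LOCF recovers [0.3(1 − mC) − 0.2(1 − mI)]/0.10. For the model, each arm's fall is (1 − s)/(1 − s·m).

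| Untested stoppers, control / reminded | LOCF | Model without statin status |
|---|---|---|
| 50% / 50% | 50% | 65% |
| 50% / 25% | 0% | 19% |
| 60% / 30% | −20% | −3% |
| 25% / 50% | 125% | 132% |

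LOCF can shrink, remove, reverse or enlarge the contrast. A model that ignores statin status does not cure this, and in the last row it does worse than LOCF.

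**The case against.** The strongest reply is that month 12 is tied to the extension throughout: in the study description, in the continuation measures and in the separate final report. On this view the LOCF sentence mainly aligns irregular real-world visits to common points, and only extension participants would receive a month-12 value. That reading is plausible, but the LOCF sentence does not state it. A reader might infer that some sites decline the extension. Nothing in the protocol says so, and with full participation Part 1 has no effect.

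For stoppers, the General description of the study says that subjects will come for final examinations in both phases, with no restriction to one arm or to statin takers. This may reduce the untested share well below the assumed 50%. It stands as a limit on the size of the problem. It does not remove it, because no lipid test is stated for that examination and Time points of assessments only recommends the month 11 to 12 visit.

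A reader might also infer that LOCF distorts the compliance results or favours one arm. Neither is supported. Nothing shows that continuation, statin duration, Morisky-Green scores or events are carried forward. No month-12 between-arm lipid test is spelled out, and the direction depends on unknown testing rates.

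Finally, analysis sets and visit windows usually belong in the SAP, which is not shown, so their absence here is not the point. The point is a rule that the protocol does state.

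**Conclusion.** The point holds in a limited form. The protocol fixes LOCF to month 12 without restricting it to extension participants, and its follow-up arrangements allow that rule to label older values as month 12 and to keep on-statin values for untested stoppers.

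The first effect is conditional on a site not joining. The second is conditional on stoppers going untested after an on-statin test; in the 20% stopping illustration it ranges from 0% to 12.5%. All stopping, testing and lipid-return rates are assumed, so neither the actual size nor the direction between arms can be stated. The effect is confined to lipids and similar repeated measures. Part 1 does not touch the 6-month report. It should be fixed, because the literal rule can mislead and the repair uses data already collected.

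**What to change.** In Data management and analysis:

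1. State that no value is carried to month 12 for sites outside the extension, and base month-12 summaries and comparisons on all patients randomised at extension sites.
2. Replace LOCF as the main method with multiple imputation by arm, using observed lipids and recorded statin status (continuing or stopped, and duration), so that untested stoppers are imputed from tested stoppers. A repeated-measures model that assumes missing at random without statin status is not an adequate replacement.
3. Add a return-to-baseline sensitivity analysis for stoppers and lost patients without a later test. Keep LOCF at most as a further sensitivity analysis.
4. As a minor clarification, say that the month 3 to 4 visit supplies the month-3 value. With a strict cut-off at month 3, a test taken after that date would be passed over for the month 1 to 2 value.

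**Cost.** This changes wording and adds some analysis work; visits and care are unchanged, and month 6 keeps all sites. The month-12 sample may be smaller and is self-selected. With k centres of equal size, intervals widen by √(6/k): about 1.10, 1.22 or 1.41 times for 5, 4 or 3 centres. The imputation assumes that untested stoppers resemble tested ones, and statin status will be unknown for some lost patients. Return to baseline understates the fall if lipids return only part way (by 5.6% in the half-return example), so it should be shown beside the main result.
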